### **14.2. Pregnancy and In Utero Drug Exposure**

The investigator will attempt to collect pregnancy information if a female patient or a male patient's female partner becomes pregnant while the patient is participating in this study. The pregnancy information will be recorded on the appropriate form and must be submitted to the Sponsor within 2 weeks of learning of the pregnancy. The patient or partner will be followed for the outcome of the pregnancy. Information on the status of the mother and child will be

forwarded to the Sponsor or designee. Generally, follow up will be no longer than 6 to 8 weeks following the estimated delivery date. Any premature termination of the pregnancy will be reported.

### **14.3. Severity**

Investigators must evaluate the severity/intensity of AEs according to the current active minor version of the National Cancer Institute Common Toxicity Criteria for Adverse Events, version 4.0 (NCI-CTCAE v4.0), preferentially using the graded scales. If there is a change in severity of an adverse event, it must be recorded as a separate event. If a particular AE's severity/intensity is not specifically graded, the investigator should apply the general guidelines for determination of Grade 1 through Grade 5 as listed in the NCI-CTCAE v4.0 cover page (as shown below), using their best medical judgment:

**Grade 1:** Mild; asymptomatic or mild symptoms; clinical or diagnostic observations only; intervention not indicated.

**Grade 2:** Moderate; minimal, local or noninvasive intervention indicated; limiting age-appropriate instrumental activities of daily living (preparing meals, shopping for groceries or clothes, using the telephone, managing money, etc.).

**Grade 3:** Severe or medically significant but not immediately life-threatening; hospitalization or prolongation of hospitalization indicated; disabling; limiting self-care activities of daily living (bathing, dressing and undressing, feeding self, using the toilet, taking medications, and not bedridden).

**Grade 4:** Life-threatening consequences; urgent intervention indicated.

**Grade 5:** Death related to AE.

### **14.4. Relationship to Study Drug**

Investigators must also assess the causal relationship of each AE to ACE-536. Factors for the assessment of causal relationship include, but are not limited to, temporal relationship between the AE and the administration of ACE-536, known side effects of ACE-536, medical history, concomitant therapy, course of the underlying disease and pertinent study procedures.

**Probable:** A causal relationship is clinically/biologically highly plausible and there is a plausible time sequence between onset of the AE and administration of ACE-536 and there is a reasonable response on withdrawal.

**Possible:** A causal relationship is clinically/biologically plausible and there is a plausible time sequence between onset of the AE and administration of ACE-536.

**Unlikely:** A causal relationship is improbable and another documented cause of the AE is most plausible.

**Unrelated:** A causal relationship can be definitively excluded and another documented cause of the AE is most plausible.

## **14.5. Documentation and Methods of Reporting of Adverse Events by Investigator**

It is the responsibility of the Investigator to document all adverse events that occur during the study. Patients will be evaluated and questioned generally for AEs during the course of the study, starting at the signing of the informed consent. The Investigator must report in detail all adverse signs and symptoms which are either volunteered by subjects or observed during or following the course of investigational product administration on the appropriate CRF page. All non-serious AEs occurring after signing of the ICF until a patient is dosed on Cycle 1 Day 1 are to be documented on the medical history CRF. All AEs and SAEs occurring after the Cycle 1 Day 1 dose through 84 days after the last study drug administration (End of Study visit) are to be reported and documented on the AE CRF.

All AEs spontaneously reported by the patient and/or in response to an open question from study personnel or revealed by observation, physical examination or other diagnostic procedures will be recorded on the AE CRF. Any clinically relevant changes in laboratory assessments, or other clinical findings as described in [Section 14.1](#), are considered AEs and must be recorded on the AE CRF. AEs are to be followed for resolution as described in [Section 14.6](#).

It is important that each AE report include a description of the event, duration (onset and resolution dates), severity, relationship with ACE-536, any other potential causal factors, any treatment given or other action taken (including dose modification or discontinuation of ACE-536) and outcome. In addition, serious AEs (SAEs) should be identified and the appropriate seriousness criteria documented. AEs categorized as SAEs must also be documented using an SAE Report Form as described in [Section 14.5.1](#).

Specific guidance can be found in the CRF Completion Guidelines provided by the Sponsor or designee.

### **14.5.1. Documentation of Serious Adverse Events**

All SAEs that occur after the first study drug administration on Cycle 1 Day 1 until 84 days after the last study drug administration (End of Study visit) are to be documented on the AE CRF. SAEs should not be reported for patients who are considered screen failures unless the event is deemed due to a protocol required procedure.

For all SAEs, an SAE form must be completed with as much information as possible and submitted within the time frame described in [Section 14.7](#) (Notification about Serious Adverse Events).

When new significant information is obtained as well as when the outcome of an event is known, the investigator should record the information on a new SAE form. If the patient was hospitalized, a copy of the discharge summary must be included as part of the patient medical file. In all instances, the investigator should follow up with patients until the outcome of the SAE is known.

## **14.6. Reporting Period and Monitoring of Patients with Adverse Events**

As described in [Section 14.5](#), all AEs must be recorded in the CRF up until the end of the treatment period. All patients who took at least one dose of study drug, whether they completed the treatment period or not, should complete the end of treatment procedures.

All AEs will be followed until clinical database lock (or resolution if it occurs before database lock). All SAEs will undergo active follow up until resolved or the event becomes chronic or stable. Follow up data for SAEs obtained after clinical database lock will be incorporated into the ACE-536 safety database.

## **14.7. Notification about Serious Adverse Events**

If an SAE occurs during the reporting period, the investigator must immediately, within a maximum 24 hours after becoming aware of the event, inform the sponsor via the CRO by telephone, fax, or e-mail.

All written reports should be transmitted using the study specific SAE Report Form, which must be completed by the investigator following specific completion instructions. Names, addresses, telephone and fax numbers for SAE reporting are located on the SAE Report Form and in the completion instructions provided in the Study Manual. When an SAE (or follow up information) is reported by telephone, a written report must be sent immediately thereafter by fax or e-mail. Reporting procedures and timelines for follow up information are the same as for the initially reported SAE.

Relevant pages from the CRF may be provided in parallel (e.g., medical history, concomitant therapy). In all cases, the information provided in the SAE Report Form must be consistent with the data that are recorded in the corresponding sections of the CRF.

The investigator/reporter must respond to any request for follow up information or to any question the Sponsor or designee may have on the AE within the same timelines as described for initial reports. This is necessary to permit a prompt assessment of the event by the Sponsor and (as applicable) to allow the Sponsor to meet regulatory timelines associated with expedited reporting obligations.

Requests for follow up will usually be made by the responsible clinical research associate or Medical Monitor, or an Acceleron pharmacovigilance representative who may contact the investigator directly to obtain clarification on a particularly critical event.

### **14.7.1. Safety Reporting to Health Authorities, Independent Ethics Committees Institutional Review Boards and Investigators**

The Sponsor will send appropriate safety notifications to Health Authorities in accordance with applicable laws and regulations.

The investigator must comply with any applicable site-specific requirements related to the reporting of SAEs involving his/her patients to the IEC that approved the study.

In accordance with International Conference on Harmonization (ICH) Good Clinical Practice (GCP) guidelines, the Sponsor will inform the investigator of “findings that could adversely affect the safety of patients, impact the conduct of the study, or alter the IEC’s approval/favorable opinion to continue the study.”

The Sponsor will inform the investigator of AEs that are both serious and unexpected and are considered to be related to ACE-536 (“suspected unexpected serious adverse reactions” or SUSARs). The investigator should place copies of these Safety Reports in the Investigator Site File. National regulations with regard to Safety Report notifications to investigators will be followed.

When specifically required by regulations and guidelines, the Sponsor will provide appropriate Safety Reports directly to the concerned lead IEC and will maintain records of these notifications. When direct reporting by the Sponsor is not clearly defined by national or site-specific regulations, the investigator will be responsible for promptly notifying the concerned IEC of any Safety Reports and for filing copies of all related correspondence in the Investigator Site File.

For studies covered by the European Union Clinical Trials Directive 2001/20/EC, the Sponsor's responsibilities regarding the reporting of SAEs/SUSARs will be carried out in accordance with that Directive and with the related Detailed Guidances.

## 15. STATISTICS

### 15.1. Analysis Populations

For all analysis populations, patients will be analyzed according to assigned treatment groups.

**The Intent-to-Treat Population:** All patients enrolled in the study who have received at least one dose of ACE-536 (Safety Population).

**Efficacy Evaluable Population:** All patients who received at least one dose of ACE-536 and have 1) at least two hemoglobin assessments  $\geq$  14 days apart post-treatment OR 2) at least 8 consecutive weeks of transfusion frequency data between Cycle 1 Day 1 and End of Treatment visit in transfusion dependent patients.

**Safety Population:** All patients who received at least 1 dose of ACE-536.

**Pharmacokinetics Population:** All patients who have received at least 1 dose of ACE-536 and have sufficient pharmacokinetic samples collected and assayed for PK analysis.

### 15.2. Statistical Plan

Summary statistics will be presented for continuous/quantitative variables, by way of number of patients (n), mean, standard deviation (SD), median, minimum and maximum and by way of group frequencies and percentages for categories of qualitative variables. Percentages will be calculated using the total patients per treatment / subgroup. 95% confidence intervals (CIs) will be presented as applicable.

All patient data will be presented in separate data listings.

#### 15.2.1. Patient Accountability and Demographics

Exposure to study drug and reasons for discontinuation of study will be tabulated, and demographics will be presented using descriptive statistics (i.e., mean, standard deviation, median, and range).

#### 15.2.2. Primary Efficacy Analysis

The **primary efficacy endpoint** is modified erythroid response (mHI-E), defined as the proportion of patients who have a hemoglobin increase of  $\geq$  1.5 g/dL from baseline for  $\geq$  14 days (in the absence of RBC transfusions) in non-transfusion dependent patients, or, a reduction of either  $\geq$  4 units or  $\geq$  50% of units of RBCs transfused over a period of 8 consecutive weeks, compared to the number of units of RBCs transfused in the 8 weeks immediately prior to Cycle 1 Day 1 in transfusion dependent patients (defined as having received  $\geq$  4 units of RBCs within 8 weeks prior to Cycle 1 Day 1). The erythroid response will be summarized using both a point estimate and its exact 95% confidence interval based on binomial distribution. The primary efficacy analysis will be performed using the EE population.

No direct comparison testing with concurrent or historical controls will be performed.

Baseline hemoglobin will be the average of at least two measures (not influenced by transfusion within 7 days of measurement); one measure performed within one day prior to Cycle 1 Day 1 and the other performed 7-28 days prior to Cycle 1 Day 1.

### 15.2.3. Secondary Analysis

**Safety analysis:** To assess clinical safety, adverse events, vital sign measurements and clinical laboratory information will be summarized. Adverse Events will be coded using the Medical Dictionary for Regulatory Activities (MedDRA). Changes from baseline for clinical laboratory values and vital signs will be summarized over time. Descriptive statistics and shift tables will be generated as appropriate.

**Secondary efficacy/pharmacodynamic analysis** of the study will be performed using the ITT and EE populations and will include:

- Modified erythroid response (mHI-E), as described above for primary endpoint, performed using the ITT population.
- HI-E response rate as defined by IWG 2006 criteria ([Appendix 5](#)). Improvements must last  $\geq$  8 weeks. For non-transfusion dependent patients, an increase of  $\geq 1.5$  g/dL from pre-treatment hemoglobin. For transfused patients, a reduction by  $\geq 4$  units of RBCs transfused (for a hemoglobin  $\leq 9.0$  g/dL) during any 8-week period on study, compared with the 8-week period prior to Cycle 1 Day 1.
- Time to mHI-E and HI-E response and duration of mHI-E and HI-E response as per the IWG 2006 criteria.
- Frequency of RBC transfusion, and rate of RBC transfusion independence in transfusion dependent patients.
- Other pharmacodynamic (PD) endpoints including:
  - Biomarkers for iron metabolism
  - Biomarkers for bone metabolism
  - Relationship of biomarkers to response
  - Rates of HI-N and HI-P

**Exploratory endpoints** will include:

- Evaluation of biomarkers related to the TGF $\beta$  superfamily.
- Evaluation of self-reported quality of life in the expansion cohort using tools including but not limited to the FACT-An questionnaire.

All binary endpoints will be summarized using both a point estimate and its exact confidence interval based on the binomial distribution. The time-to-event type secondary endpoints will be analyzed using Kaplan-Meier method to estimate the survival curve and median time to event and 95% confidence interval.

#### **15.2.4. Pharmacokinetics Analysis**

**Pharmacokinetics analysis:** Non-compartmental PK parameters for ACE-536, such as maximum plasma concentration ( $C_{max}$ ), time to maximum plasma concentration ( $t_{max}$ ), and area under the concentration/time curve (AUC), will be estimated. Dose proportionality may be assessed using the exposure data (e.g.  $C_{max}$ , AUC) after the first dose if sufficient dose levels are studied. Descriptive statistics will be provided for serum concentrations and PK parameters. The relationship between ACE-536 exposure and response (i.e., safety, efficacy, and biomarkers) may be explored, if appropriate.

#### **15.2.5. Anti-drug Antibody Analysis**

**Anti-drug antibody analysis:** The results of anti-drug and neutralizing antibody testing for ACE-536 and human ActRIIB protein versus time will be presented. Exploratory analysis will be performed on the potential effect of anti-drug antibodies on ACE-536 PK and drug exposure if anti-drug antibody tests are deemed positive.

### **15.3. Determination of Sample Size**

There is no formal sample size calculation for the dose escalation portion of the study. A standard dose escalation design will be implemented, and up to 42 patients will be enrolled at up to 7 different dose levels to further evaluate erythroid response.

A sample size of 30 evaluable patients in expansion cohort 1 will provide approximately 90% power with 1-sided significance level of 0.05 to differentiate an erythroid response rate of 30% from a minimal erythroid response rate of 10% based on Fisher exact test.

A sample size of 25 evaluable patients in each group of expansion cohort 2 will provide approximately 80% power with 1-sided significance level of 0.05 to differentiate an erythroid response rate of 30% from a minimal erythroid response rate of 10 % based on Fisher exact test.

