### Statistical methods

#### Sample Size Calculation:

There is no formal sample size calculation for the dose escalation portion of the study. A sample size of 30 evaluable patients in the expansion cohort 1 will provide approximately 90% power with 1-sided significance level of 0.05 to differentiate an erythroid response rate of 30% from a minimal erythroid response rate of 10% based on Fisher exact test.

A sample size of 25 evaluable patients in each group of expansion cohort 2 will provide approximately 80% power with 1-sided significance level of 0.05 to differentiate an erythroid response rate of 30% from a minimal erythroid response rate of 10% based on Fisher exact test

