### 9.1. Study Design

Patients who meet the study eligibility criteria will be enrolled within 28 days of screening. Patients in all cohorts will receive ACE-536, administered subcutaneously (SC), every 3 weeks for up to 5 cycles. Dose delay(s) and dose reduction(s) may be required for individual patients as outlined in the Patient Dose Modification Rules ([Section 10.8.1](#)).

Each dose escalation cohort will consist of a minimum of 3 patients. The dose level of ACE-536 for the first cohort will be 0.125 mg/kg and the dose level(s) for subsequent cohort(s) will follow a modified Fibonacci dose escalation scheme with a maximum dose level of 0.25 mg/kg for cohort 2, 0.50 mg/kg for cohort 3, 0.75 mg/kg for cohort 4, 1.0 mg/kg for cohort 5, 1.33 mg/kg for cohort 6, 1.75 mg/kg for cohort 7, and a maximum dose level not to exceed 1.75 mg/kg. Once a minimum of 3 patients in a cohort have completed Study Day 29, the Safety Review Team (SRT) will review preliminary safety and hematologic response data and make recommendations to the Sponsor regarding whether or not to enroll an additional 3 patients in that cohort, enroll a new cohort at a higher or lower dose, or proceed to expansion cohort 1.

Expansion cohort 1 (n= approximately 30) will be treated with ACE-536 at a starting dose level of 1.0 mg/kg. Expansion cohort 1 will consist of a minimum of 10 patients who are transfusion dependent (TD) and 10 patients who are non-transfusion dependent (NTD), if feasible.

Expansion cohort 2 will be treated with ACE-536 at a starting dose level of 1.0 mg/kg. Expansion cohort 2 will be divided into two groups designated expansion cohort 2A and 2B. The targeted accrual for each group will be 25 eligible and evaluable patients but permitted to range from 22 to 28 for administrative reasons. The maximum number of patients treated will be 56.

- Expansion cohort 2A: NTD patients with  $\geq 15\%$  ring sideroblasts in the bone marrow (RS+), less than 4 weeks of exposure to erythropoietin stimulating agents (ESAs) and serum erythropoietin (EPO) level  $\leq 200$  U/L at screening.
- Expansion cohort 2B: Patients with  $< 15\%$  ring sideroblasts in the bone marrow (RS-) and  $\leq 6$  RBC units in 8 weeks prior to C1D1. This group will consist of a minimum of 10 patients who have less than 4 weeks of exposure to ESAs and 5 patients who have received  $\geq 4$  weeks of treatment with ESAs.

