3.3. Sample Size

There is no formal sample size calculation for the dose escalation portion of the study. A standard dose escalation design will be implemented, and up to 42 patients will be enrolled at up to 7 different dose levels to further evaluate erythroid response.

A sample size of 30 evaluable patients in the expansion cohort will provide approximately 90% power with 1-sided significance level of 0.05 to differentiate an erythroid response rate of 30% from a minimal erythroid response rate of 10% based on Fisher exact test.

A sample size of 25 evaluable patients in each group of expansion cohorts 2 and 3 will provide approximately 80% power with 1-sided significance level of 0.05 to differentiate an erythroid response rate of 30% from a minimal erythroid response rate of 10 % based on Fisher exact test.

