5.2. General Considerations

Unless otherwise noted, continuous data will be summarized with the following descriptive statistics: number of observations (n), mean, standard deviation (STD), minimum, median, and maximum. Categorical data will be summarized with frequencies (n) and percentages (%). In cases where missing data cause percentages not to sum to 100, a missing data row will be provided. Percentages will use column totals as the denominator unless otherwise indicated. For time to event variables, the Kaplan-Meir curves will be presented if the number of patients is more than 5.

All data in the database will be used in the analysis, with the exception of exclusions defined in section 5.7 for efficacy analyses. All study data will be included in study data listings. Missing data will generally not be imputed, unless otherwise stated.

All summaries will be presented by dose cohort, and may also be presented for LTB and HTB patients separately as specified. All summaries will be descriptive. No formal hypothesis testing is planned.

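### Expansion cohort 1: 30 patients give about 84% exact power, not the stated 90%, and Fisher's exact test does not fit a single arm compared with a fixed 10%

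*Protocol*

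**What the plan says.** Protocol 15.3 justifies the size of expansion cohort 1 in one sentence, which opens with the claim "A sample size of 30 evaluable patients in expansion cohort 1 will provide approximately 90% power with 1-sided significance level of 0.05". The sentence then gives the aim and the method of the calculation: "to differentiate an erythroid response rate of 30% from a minimal erythroid response rate of 10% based on Fisher exact test". The synopsis has the same sentence ("A sample size of 30 evaluable patients in the expansion cohort 1 will provide approximately 90% power with 1-sided significance level of 0.05"). SAP 3.3 repeats it without the cohort number ("A sample size of 30 evaluable patients in the expansion cohort will provide approximately 90% power with 1-sided significance level of 0.05").

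The next sentence in each place uses the same rates, alpha and test to claim approximately 80% power for 25 evaluable patients per group of expansion cohort 2. SAP 3.3 extends that sentence to cohort 3. Protocol 9.1 lets the cohort 2 groups vary in size: "The targeted accrual for each group will be 25 eligible and evaluable patients but permitted to range from 22 to 28 for administrative reasons".

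Three other statements bear on the point:

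- There is no control arm (Protocol 9.1): "Patients in all cohorts will receive ACE-536, administered subcutaneously (SC), every 3 weeks for up to 5 cycles". Protocol 10.4 confirms that there is no randomization.
- Protocol 15.2.2 says: "No direct comparison testing with concurrent or historical controls will be performed". The primary endpoint is reported as a proportion with an exact binomial 95% interval.
- SAP 5.2 says: "All summaries will be descriptive. No formal hypothesis testing is planned".

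**The concern.** Two things do not fit together. First, Fisher's exact test needs two sampled groups. Cohort 1 is a single treated group and the 10% is a fixed benchmark, so there is no second row for the 2×2 table. Second, 90% looked too high for 30 patients under any exact test of 30% against 10% that holds one-sided alpha at 0.05.

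This sentence is the only quantitative reason given for the size of cohort 1. If it is wrong, the chance of missing a true 30% response rate is larger than the reader is told, and the figure cannot be recovered from the method named beside it.

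**Working it through.** **Inputs** (Protocol 15.3): n = 30; null rate p0 = 0.10; alternative p1 = 0.30; one-sided alpha 0.05; stated power about 90%. Companion figure: n = 25, about 80%.

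**Can the 90% be reproduced?**

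- *Fisher's test taken literally*, two arms of 30 at 10% and 30%: power 48.9%. No.
- *Fisher's test against a very large reference sample at 10%* (1,000 or more): power 84.05%, the same as the one-sample binomial test. No.
- *One-sample normal approximation, no continuity correction*: power = Φ[(p1 − p0 − 1.645·√(p0(1−p0)/n)) / √(p1(1−p1)/n)]. At n = 30 this is Φ[(0.20 − 1.645 × 0.05477)/0.08367] = Φ(1.314) = 90.6%. This matches the stated 90%. With continuity correction it is 86.7%.
- *Arcsine approximation*: power = Φ[2(arcsin√0.30 − arcsin√0.10)·√n − 1.645]. At n = 30 this is Φ(0.5158 × 5.477 − 1.645) = 88.1%.

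The stated figure is therefore consistent with a large-sample formula. The documents do not say which was used.

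**Exact one-sample binomial test.** Take the smallest cut-off c with P(X ≥ c | n, 0.10) ≤ 0.05. Power is P(X ≥ c | n, 0.30).

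| n | Reject at | Attained alpha | Power at 30% |
|---|---|---|---|
| 30 | ≥6 | 0.073 (exceeds 0.05) | 92.3% |
| 30 | ≥7 | 0.026 | **84.0%** |
| 33 | ≥7 | 0.042 | 90.6% |
| 25 | ≥6 | 0.033 | 80.7% |

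At n = 30 no cut-off gives about 90% power within alpha 0.05. The shortfall is 90 − 84.0 = 6 points, so the type II error is 16%, not 10%. With the ≥7 rule, 90% power at n = 30 needs a true rate of about 32.5%. The first n with at least 90% exact power is 33. Power drops below 90% again at n = 35 and 36, where the cut-off moves to 8, and returns above it from n = 37.

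**Why the approximation does not rescue the sentence.** The normal-approximation cut-off at n = 30 is 30 × (0.10 + 1.645 × 0.05477) = 5.70 responders, so it rejects at 6 or more, where the true alpha is 0.073. At n = 25 the same formula gives 86.6%, which does not match the 80% stated in the next sentence; the exact test does (80.7%).

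**Permitted range for the cohort 2 groups, same exact test:**

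| n | 22 | 23 | 24 | 25 | 26 | 27 | 28 |
|---|---|---|---|---|---|---|---|
| Cut-off | 6 | 6 | 6 | 6 | 6 | 6 | 7 |
| Power | 68.7% | 73.1% | 77.1% | 80.7% | 83.7% | 86.4% | 78.0% |

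The drop at 28 comes from the cut-off stepping up from 6 to 7.

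**The case against.** The strongest reply is that the text says approximately, and that ordinary approximations come near it: the normal formula gives 90.6% at n = 30, and the arcsine formula gives 88.1% at n = 30 and 82.5% at n = 25, close to both stated figures. The name Fisher may simply be loose usage for an exact test. This stands as a likely explanation of the number, and it means the 90% is irreproducible only under an exact method. It does not make the sentence correct. An exact test is named, and the approximations ignore the discreteness that costs power at n = 30. A section that distinguishes 80% from 90% also cannot count 84% as 90%.

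The second reply is that nothing depends on the figure: no formal test is planned and no success threshold uses it. That is right, and it limits the consequence to the justification.

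The third is that 84% does not describe the planned reporting either. The planned interval is two-sided 95%. At 7/30 its exact lower limit is 9.93%, which does not exclude 10%; 8/30 is needed, with 71.9% power. SAP 5.7.1 also reports low and high transfusion burden patients separately, whereas the calculation pools all 30. Both observations are fair. They call for a clear label on the restated figure, not for keeping the 90%.

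The fourth is that power over 22 to 28 patients is optional detail, since the 80% is correct at the target of 25. That is accepted; the point does not rest on it.

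**Conclusion.** The sentence is wrong as written. For 30 evaluable patients, 30% against a fixed 10%, and one-sided alpha 0.05, exact power is 84.0%, about 6 points below the stated figure, and the named test has no second sample to work on. The n = 25 figure is correct in size but carries the same wrong test name.

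The conclusion assumes that all 30 patients are evaluable and analysed as one group, and that the nominal test is the exact one-sample binomial at the stated alpha. Under an uncorrected normal approximation the 90% would be recovered, but with a true type I error of 7.3% at the rejection rule it implies. No efficacy estimate, interval or planned table is affected. The point merits correction, with consequences limited to the sample-size justification.

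**What to change.** In Protocol 15.3, the synopsis and SAP 3.3:

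- Replace the reference to Fisher's test with the one-sample exact binomial test against a fixed 10%.
- State about 84% power for n = 30 (reject at ≥7/30, attained alpha 0.026).
- State about 81% for n = 25 (reject at ≥6/25, attained alpha 0.033). In SAP 3.3 keep this sentence covering cohort 3 as well as cohort 2, and name cohort 1 in the 30-patient sentence.
- Say that these are powers of a nominal one-sided test on the pooled cohort, given to justify its size, and that no such test will be performed.

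Optionally, add that exact power runs from 69% to 86% over the permitted 22 to 28 patients per cohort 2 group.

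The cost is wording in three places and a stated power about 6 points lower for cohort 1. No patients, analyses or tables are added. Had 90% exact power been a firm requirement, the smallest qualifying size would have been 33 evaluable patients.
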